9.1.3. Multiplicity Considerations

All the primary immunogenicity endpoints/estimands are considered coprimary in the study. For the primary immunogenicity objectives comparing immune responses induced by vaccine antigens from the MenABCWY group(s) to that from the comparator group(s), noninferiority is assessed by hypothesis tests as stated in [Section 9.1.2](#), at a 2-sided level of 0.05 for each of the endpoints. The primary immunogenicity objectives will be met if noninferiority is achieved for each endpoint. Therefore, the type I error rate for the immunogenicity assessment is well controlled at the 0.05 level. If the primary objectives are met, then testing of noninferiority for all the secondary endpoints related to seroresponders who achieve a 4-fold rise at 1 month after Vaccination 1 will be done at the 0.05 level.

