9.2. Sample Size Determination

9.2.1. Immunogenicity Subset (Groups 1-4)

[Table 7](#) and [Table 8](#) present the power to demonstrate that the immune response induced by 2 doses of MenABCWY is noninferior to the immune response induced by 1 dose of MenACWY-CRM for ACWY-naïve and ACWY-experienced participants, respectively, and [Table 9](#) presents the power to demonstrate that the immune response induced by 2 doses of MenABCWY is noninferior to the immune response induced by 2 doses of Trumenba. The study is powered based on a combined (product) power across both the primary objectives.

Noninferiority comparisons will be based on the 4-fold rises and also composite response for the MenB endpoints (at 1 month following Vaccination 2) and seroresponders who achieve a 4-fold response for the ACWY endpoints (at 1 month after Vaccination 2 for Groups 1 and 3 and at 1 month after Vaccination 1 for Groups 2 and 4). The lower bounds of the corresponding 95% CIs of the group differences will be compared to the noninferiority criterion (-10%).

With 360, 180, 540, and 270 evaluable participants in Groups 1, 2, 3, and 4, respectively, and the assumptions in the tables below, the power is:

- above 99.9% to demonstrate noninferiority for the first primary objective relating to the ACWY response in ACWY-naïve participants,
- above 99.4% to demonstrate noninferiority for the first primary objective relating to the ACWY response in ACWY-experienced participants, and
- above 91.6% for the second primary objective relating to the MenB response.

The combined power, across both primary objectives, is above 91.0%. Therefore, assuming a nonevaluable rate of 20%, 450, 225, 675, and 338 participants in Groups 1, 2, 3, and 4, respectively, will be enrolled to have sufficient evaluable participants.

Some participants may be moved from the safety subset to the immunogenicity subset as described in [Section 4.1](#). The sponsor may decide to proceed with less than full enrollment if an assessment of power shows that it is sufficient (<91% with full enrollment but still >85%) to meet the primary objectives. This assessment will be done in a completely blinded fashion before any participants are unblinded or the immunogenicity data are accessed.

Table 7. Power Analysis for First Primary Immunogenicity Objective (ACWY-Naïve Participants)

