9.4.1. Immunogenicity Analyses

Primary	
For each of the 4 ACWY test strains, the difference in the percentages of seroresponders, defined as participants achieving a 4-fold rise from baseline, in Group 1 at 1 month after Vaccination 2 compared to Group 2 at 1 month after Vaccination 1, and also the difference in seroresponders in Group 3 at 1 month after Vaccination 2 compared to Group 4 at 1 month after Vaccination 1, will be calculated.
 
For each of the 4 primary MenB test strains, the differences of the 4-fold rises and composite responses of Groups 1 and 3 combined compared to Groups 2 and 4 combined at 1 month after Vaccination 2 will be calculated.
 
The Miettinen and Nurminen method will be used to derive the CI for the difference in percentages between vaccine groups. The lower limit of the CI will be used in the hypothesis test for noninferiority as detailed in Section 9.1.
 
The analysis for the ACWY test strains is based on the post-Vaccination 1 evaluable population for Groups 2 and 4 and on the post-Vaccination 2 evaluable population for Groups 1 and 3 and the analysis for the primary MenB strains is based on the post-Vaccination 2 evaluable population in order to provide a comparison that has the greatest chance of identifying a difference between the groups with respect to immunogenicity, if a meaningful difference in vaccine effect actually exists.
 
Exact 2-sided 95% CIs for the percentages (seroresponders, 4-fold-rises and composite responses) will be provided using the Clopper-Pearson method.
 
A supportive analysis will be performed based on the modified intent-to-treat (mITT) population. Participants will be summarized according to the vaccine group to which they were randomized. Missing serology data will not be imputed.

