5. GENERAL METHODOLOGY AND CONVENTIONS

5.1. Hypotheses and Decision Rules

The primary immunogenicity objectives are:

- To demonstrate that the immune response for MenA, MenC, MenW, and MenY induced by 2 doses of MenABCWY is noninferior to the immune response induced by 1 dose of MenACWY-CRM, for ACWY-naïve and ACWY-experienced participants separately.
- To demonstrate that the immune response for MenB induced by 2 doses of MenABCWY is noninferior to the immune response induced by 2 doses of Trumenba.

The primary objectives of noninferiority will be met if:

- The lower limit of the 2-sided 95% CI for the difference in seroresponders (Group 1 - Group 2) is $> -10\%$ for all of the MenACWY test strains at 1 month after the second vaccination for Group 1 and at 1 month after the first vaccination for Group 2; and
- The lower limit of the 2-sided 95% CI for the difference in seroresponders (Group 3 - Group 4) is $> -10\%$ for all of the MenACWY test strains at 1 month after the second vaccination for Group 3 and at 1 month after the first vaccination for Group 4; and
- The lower limit of the 2-sided 95% CI for the differences in 4-fold rises and composite responses (Groups 1+3 - Groups 2+4) is $> -10\%$ for all of the primary MenB test strains at 1 month after the second vaccination.

For the MenACWY noninferiority evaluation in ACWY-naïve participants, the immune response will be evaluated at 1 month following Vaccination 2 for Group 1 and at 1 month following Vaccination 1 for Group 2. The null hypothesis (H_0) for each MenACWY serogroup for noninferiority is as follows:

$$H_0: \pi_{G1} - \pi_{G2} \leq -10\%$$

where π_{G1} and π_{G2} are the percentages of participants who achieve a 4-fold rise in hSBA titers for MenA, MenC, MenW, and MenY.

π_{G1} and π_{G2} represent Group 1 and Group 2 participants, respectively.

For the MenACWY noninferiority evaluation in ACWY-experienced participants, the immune response will be evaluated at 1 month following Vaccination 2 for Group 3 and at 1 month following Vaccination 1 for Group 4 participants.

The null hypothesis (H_0) for each MenACWY serogroup for noninferiority is as follows:

$$H_0: \pi_{G3} - \pi_{G4} \leq -10\%$$

where π_{G3} and π_{G4} are the percentages of participants who achieve a 4-fold rise in hSBA titers for MenA, MenC, MenW, and MenY.

π_{G3} and π_{G4} represent Group 3 and Group 4 participants, respectively.

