5.3.2. Immunogenicity Data

As assay data are expected to be missing completely at random, the primary analysis for the primary objectives will be based upon the observed, determinate observations. No imputation will be performed. The proportion of participants with missing immunogenicity data may be summarized at each blood sampling visit for each MenB and MenACWY strain. The denominator will be the as-randomized population. The category of missing reasons (QNS, indeterminate, not done, dropout) may also be summarized.

If 10% or more of the participants in any group have missing hSBA data for the MenB or MenACWY strains for non-withdrawal-related reasons, a sensitivity analysis using an MMRM in the immunogenicity subset may be applied for each strain (GMT). For the MenACWY strains, the ACWY-naïve and ACWY-experienced participants will be analyzed separately. For the primary MenB strains, Groups 1 and 3 combined will be described against Groups 2 and 4 combined.

The MMRM uses maximum likelihood estimation and it is under the assumption that the missingness is at random (MAR). To account for the intraparticipant correlation among the repeated measures, an unstructured covariance matrix will be used. In case the model does not converge, further covariance structures will be explored (ie, first-order autoregressive, compound symmetry). Independent variables (race, sex, etc) may be dropped from the model because of nonconvergence.

$\text{Log (hSBA)} = \text{randomized group(s)} + \text{race} + \text{sex} + \text{geographic location (US; ex-US)} + \text{age at randomization} + \text{visit}$. The intercept will be set as random effect.

In addition to type III analysis output, least-squares GMTs at each visit will be summarized for each strain.

These analyses will use the mITT population, using $\frac{1}{2}$ LLOQ to set the hSBA values below LLOQ.

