Similar to GMT, a GLIMMIX will be used. The response variables are binary variables (composite response and 4-fold response), and a logit link will be used. The model will be similar to above. As the 4-fold responses will not have a response at Visit 1, the GLIMMIX will use baseline hSBA titer as covariate and blood sampling time points at Visits 2 and 4 as repeated dependent variables. The composite response analyses will be similar to the GMT analyses, with composite responses at all 3 visits modeled as dependent variables. This analysis will only be applied to the mITT population. The model-estimated response rates and the 95% CIs will be summarized. The groups for the ACWY-naïve and ACWY-experienced participants will be similar to the GMT analysis.

For the hSBA assay results, the following values will be set to missing: QNS (insufficient sera), indeterminate results, and not done. Participants without blood draw (ie, dropout) will also have missing data for immunogenicity.

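### The missing-at-random check on the co-primary responses reports separate group rates, not the difference against -10%, and its listed model lacks the group-by-visit term that the ACWY contrast needs

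*SAP*

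**What the plan says.** **The primary rule.** Protocol 9.1.3 tests noninferiority "at a 2-sided level of 0.05 for each of the endpoints". Protocol 9.4.1 fixes the interval: "The Miettinen and Nurminen method will be used to derive the CI for the difference in percentages between vaccine groups". SAP 5.1 requires the lower limit to exceed -10%. For ACWY the two arms are read at different visits, "at 1 month after the second vaccination for Group 1 and at 1 month after the first vaccination for Group 2; and" likewise for Groups 3 and 4. For MenB, Groups 1+3 and 2+4 are both read at Visit 4. That makes 13 comparisons: 4 ACWY strains in naïve participants, 4 in experienced participants, 4 MenB fold-rise endpoints and the MenB composite.

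**The missing-at-random analysis.** SAP 5.3.2 bases the primary analysis on observed results, taken as missing completely at random. If at least 10% of any group lacks hSBA data for reasons other than withdrawal, a mixed model may be fitted in the mITT population.

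- For log titer, the model lists group, race, sex, location, age and visit, with a random intercept. Its output is given as "In addition to type III analysis output, least-squares GMTs at each visit will be summarized for each strain".
- For the composite and 4-fold responses, a logit GLIMMIX is described as similar to that model. Visits 2 and 4 are the repeated outcomes for the 4-fold response, with baseline titer as a covariate; all three visits are used for the composite. Its output is "The model-estimated response rates and the 95% CIs will be summarized".

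**The other sensitivity analyses.** SAP 6.1.1.1.2 and 6.1.1.2.2 repeat the ACWY main analysis in mITT. SAP 6.1.1.3.2 does so for MenB only if the populations differ by more than 10%. None of these imputes missing serology.

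**The concern.** A sensitivity analysis for missing data should answer the same question as the analysis it supports: does the lower limit of the difference stay above -10% when the missing-data assumption is relaxed? The GLIMMIX models the right responses but stops at one rate and one interval per group. The reader is left to build the difference, choose the time points and find an interval.

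For ACWY there is a second difficulty. The contrast crosses visits, and the listed model forces the same group effect (on the logit scale) at Visits 2 and 4. Groups 2 and 4 get MenACWY-CRM only at Visit 1, while Groups 1 and 3 get a second MenABCWY dose at Visit 3, so there is good reason to expect group differences to change between those visits. If they do, the modelled rates at the two co-primary time points are pulled away from the true ones.

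At stake is whether this analysis, if triggered, can be cited for or against the robustness of the noninferiority conclusion.

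**Working it through.** **Inputs from the documents.** Margin -10 points, two-sided 95% CI. Protocol 9.2.1 gives the sizes: "With 360, 180, 540, and 270 evaluable participants in Groups 1, 2, 3, and 4, respectively", hence 900 v 450 for MenB. Reference rates from Protocol Tables 7 to 9: MenC naïve 70%, MenA naïve 95.8%, MenY experienced 94.6%, B24 64.5%. Comparator ACWY rates at Visit 4 are not in the documents, so those below are assumptions.

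**1. The plan's own figure.** Power = Φ[(δ + 0.10 − 1.96·s0)/s1], with s0 the standard error at the restricted estimates under a difference of -10% and s1 the standard error under the assumed rates. For B24, δ = 0, the restricted rates are 0.6084 and 0.7084, s0 = 0.02690, and s1 = √[0.645 × 0.355 × (1/900 + 1/450)] = 0.02763. So (0.10 − 0.05273)/0.02763 = 1.711 and power is 95.65%, against 95.64% in Table 9. The five MenB powers multiply to 91.65%, against >91.63% stated. The primary test is as described and is not in question.

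**2. What separate rates show.** Two illustrative outcomes at the planned sizes, using raw counts. The rebuilt lower limit is d − √[(p1 − l1)² + (u2 − p2)²], where l1 is the lower limit for the MenABCWY rate and u2 the upper limit for the comparator rate.

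- B24, 536/900 v 290/450: rates 59.56% (56.31 to 62.72) and 64.44% (59.91 to 68.73). The intervals overlap. Difference -4.89 points; rebuilt lower limit −4.89 − √(3.25² + 4.29²) = -10.27; Miettinen-Nurminen -10.28. Noninferiority fails.
- MenY experienced, 478/540 v 255/270: rates 88.52% (85.54 to 90.95) and 94.44% (90.99 to 96.62). The intervals do not overlap. Difference -5.93 points; rebuilt lower limit -9.61; Miettinen-Nurminen -9.67. Noninferiority holds.

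Judging by overlap of the reported intervals gives the wrong impression in both directions. A reader who rebuilds the difference gets close.

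**3. The ACWY contrast from the listed model.** Take logit(p) = a + b·(Group 1) + c·(Visit 4), weights 360 and 180, complete data, other covariates and the random intercept left out. The large-sample fit matches the group totals and the visit totals. With Group 1 at 60% at both visits and Group 2 at 70% then 40%, the true contrast (Group 1 Visit 4 minus Group 2 Visit 2) is 60 − 70 = -10. The solution is a = 0.4098, b = 0.2069, c = -0.4140, so:

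- Group 1: 64.95% and 55.05% (mean 60%, as it must be).
- Group 2: 60.10% and 49.90% (mean 55%, as it must be).
- Contrast: 55.05 − 60.10 = -5.05 points.

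The same calculation under other assumed rates, with the true contrast -10 throughout:

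| Group 1, Visits 2 / 4 | Group 2, Visits 2 / 4 | Model contrast |
|---|---|---|
| 60 / 60 | 70 / 70 | -10.0 |
| 60 / 60 | 70 / 60 | -8.3 |
| 60 / 60 | 70 / 50 | -6.7 |
| 60 / 60 | 70 / 40 | -5.05 |
| 50 / 60 | 70 / 40 | -3.3 |
| 85.8 / 85.8 (MenA) | 95.8 / 70 | -5.9 |

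There is no bias when nothing changes between visits, and the bias grows with comparator waning and with a rise after dose 2. Across 4,000 simulated trials per setting (within-participant latent correlation 0.5, robust variance), the lower limit of the model contrast cleared -10% in 19.8% of trials for 60/60 v 70/40 and in 36.1% for the MenA row. The direct difference cleared it in 1.9% and 1.8%. These figures illustrate the bias and are not forecasts.

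**The case against.** **A zero-difference test is not what the SAP specifies here.** A reader might infer that the check tests the co-primaries against no difference, because SAP 5.3.2 mentions type III output. That output is named for the log-titer model. The sentence on the binary model names no hypothesis test, and describing the two models as similar does not carry the outputs across. SAP 5.1 gives type III tests no role in the decision. This part of the objection stands in full.

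**The rates are informative.** A reader might also infer that the analysis can neither support nor undermine noninferiority. That is too strong. Limits rebuilt from per-group intervals gave the Miettinen-Nurminen decision in all 722 outcomes scanned over five endpoints. But that scan used raw counts. Model rates share covariate estimates whose covariance is not reported, and with a random intercept and logit link they may be conditional rather than marginal. For ACWY they also carry the bias in step 3. MenB is easier, since both arms are read at Visit 4.

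**The -10% rule is checked elsewhere.** The mITT repeats apply it at the correct time points. True, but they use observed data only and leave the missing-at-random question open.

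**The analysis is optional and gates nothing.** Also true: it may be applied, and only past the 10% trigger. This limits the severity.

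**The bias depends on assumed rates.** It does, and with stable group differences it vanishes. However, Protocol 2.2.2.3 reports that the naïve MenC difference from a single MenACWY-CRM dose rose from 5.5 points after one MenABCWY dose to 26.5 after two. That points to a rise in Group 1 between visits, which in the table makes the bias larger.

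**Conclusion.** The point holds in a limited form. SAP 5.3.2 does not prespecify the between-group difference, its CI or the comparison with -10% for its only missing-at-random analysis of the co-primary responses, and no other planned analysis fills that gap. If the ACWY difference were taken from the model as listed, it would be biased whenever group differences change between Visits 2 and 4: by about 5 of 10 points for MenC-like rates (70% falling to an assumed 40%), 4 points for MenA-like rates (95.8% falling to an assumed 70%), and nothing if rates are stable.

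These sizes rest on assumed Visit 4 comparator rates, on Group 1 placed at the null boundary, and on a simplified model without baseline titer, other covariates or the random intercept. The documents do not support reading this as an error in the primary test, in its type I error or in the sample size; none of these changes. It is a cheap improvement.

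**What to change.** In SAP 5.3.2:

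1. Add a group-by-visit term to the binary models. It matters for the composite as well, since that model includes Visit 1, where randomised groups should not differ.
2. Replace the stated binary output with wording such as: for each of the 13 co-primary comparisons, the model-standardised (marginal) risk difference will be reported with a two-sided 95% CI, and its lower limit compared with -10%. The contrasts are Group 1 minus Group 2 and Group 3 minus Group 4, each as Visit 4 minus Visit 2, for ACWY; and Groups 1+3 minus Groups 2+4 at Visit 4 for MenB.
3. State that type III tests are not used to judge noninferiority.

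The interaction has to come with the new output. Adding the contrast to the model as listed would put a potentially biased ACWY figure beside the margin.

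The cost is SAP wording, one more model term and a standardisation step, with a small added risk of nonconvergence. The SAP already allows covariates to be dropped in that case; it should say that group, visit and their interaction are kept. No new data are needed, and no sample-size or power figure changes.

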6. ANALYSES AND SUMMARIES

[Section 2](#) describes the estimands for each of the study objectives and [Section 5.1](#) includes further details about the hypothesis testing for the primary and first secondary objectives. Below are the planned analysis by endpoints.

6.1. Primary Endpoints

6.1.1. Primary Immunogenicity Endpoints

6.1.1.1. hSBA Titer for Each of the MenACWY Test Strains for ACWY-Naïve Participants

6.1.1.1.1. Main Analysis

- Estimand strategy: Hypothetical.
- Analysis set: ACWY-naïve participants: Post-Vaccination 1 evaluable population for Group 2 and post-Vaccination 2 evaluable population for Group 1.
- Analysis methodology: 95% CI for the difference in the percentage of seroresponders (defined as participants achieving a 4-fold rise from baseline for each MenACWY test strain) calculated by the Miettinen and Nurminen procedure.
- Intercurrent events and missing data: Missing serology results will not be imputed. Participants will be summarized according to the vaccine group to which they were randomized.
- The 95% CIs for the difference in the percentage of seroresponders, defined as participants achieving a 4-fold rise from baseline for each MenACWY test strain, 1 month after Vaccination 2 in Group 1 compared to 1 month after Vaccination 1 in Group 2 will be calculated using the Miettinen and Nurminen method. The lower limit of the CI will be used in the hypothesis test for noninferiority as detailed in [Section 5.1](#). Exact 2-sided 95% CIs for the percentages of seroresponders will be provided using the Clopper-Pearson method.

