Additionally, randomization will be stratified by geographic region. The overall participant distribution by region will be approximately 80% from the US and approximately 20% from other regions. Among the participants in the immunogenicity subset, approximately 80% will be enrolled in US investigative sites, and approximately 20% will be enrolled in other regions. Regional or safety/immunogenicity group enrollment shifts may be necessary based on the availability of participants with specific characteristics (age group or ACWY experience) in a given location based on local immunization practices. However, these minor shifts from the originally targeted numbers will not deviate from original targets to a degree that will impact the overall study design or endpoint assessments of the study.

Enrollment targets will also be adjusted to achieve appropriate representation by age group (participants 10 to <18 years old and participants 18 to <26 years old) within each subset, and by MenACWY stratum within each subset.

Each participant will participate in the study for approximately 12 months. Approximately 2413 participants will be enrolled.

A portion of the projected number of participant enrollment slots may be moved from the safety subset to the immunogenicity subset to achieve appropriate regional distribution for the overall study population and the immunogenicity subset. This determination will be made by the sponsor while still blinded. The sponsor may decide to proceed with less than full enrollment if an assessment of power shows that it is sufficient to meet the primary objectives. This assessment will be done in a completely blinded fashion before any participants are unblinded or the immunogenicity data are accessed.

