The 4-fold response in assay titers from baseline (Visit 1, prevaccination) to 1 month after Vaccinations 1 and 2 (Visits 2 and 4) will be defined as follows:

- For participants with a baseline hSBA titer below the LOD (or an hSBA titer of $<1:4$), a 4-fold response is defined as an hSBA titer of $\geq 1:16$.
- For participants with a baseline hSBA titer of \geq LOD (ie, hSBA titer of $\geq 1:4$) and $<$ LLOQ, a 4-fold response is defined as an hSBA titer of ≥ 4 times LLOQ.
- For participants with a baseline hSBA titer of \geq LLOQ, a 4-fold response is defined as an hSBA titer of ≥ 4 times the baseline titer.

The 4-fold response variable for the MenB and MenACWY strains will be computed as:

- = ●, if the assay result at baseline or the specific time point is missing, indeterminate, or otherwise unavailable;
- = 1, if the assay result meets 1 of the 3 definitions for a 4-fold response;
- = 0, if the assay result does not meet 1 of the 3 definitions for a 4-fold response.

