6.1.1.3. Primary MenB Test Strain Evaluation (A22, A56, B24, and B44)

6.1.1.3.1. Main Analysis

- Estimand strategy: Hypothetical.
- Analysis set: Post–Vaccination 2 evaluable population.
- Analysis methodology: 95% CI for the difference in the percentage of the 4-fold rises and composite responses, calculated by the Miettinen and Nurminen procedure.
- Intercurrent events and missing data: Missing serology results will not be imputed. Participants will be summarized according to the vaccine group to which they were randomized.
- The 95% CIs for the difference in the percentage of participants achieving an hSBA titer \geq LLOQ (1:16 for strain A22 and 1:8 for strains A56, B24, and B44) for all 4 primary MenB test strains combined (composite response), in Groups 1 and 3 combined compared to Groups 2 and 4 combined, at 1 month after Vaccination 2 will be calculated using the Miettinen and Nurminen method. The lower limit of the CI will be used in the hypothesis test for noninferiority as detailed in [Section 5.1](#).
- The 95% CIs for the difference in the percentage of participants achieving at least a 4-fold rise in hSBA titer from baseline for each of the 4 primary MenB test strains, in Groups 1 and 3 combined compared to Groups 2 and 4 combined, at 1 month after Vaccination 2 will be calculated using the Miettinen and Nurminen method. The lower limit of the CI will be used in the hypothesis test for noninferiority as detailed in [Section 5.1](#).

Exact 2-sided 95% CIs for the percentages of participants achieving 4-fold rises, and composite responses, will be provided using the Clopper-Pearson method.

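### The five MenB primary confidence intervals leave out baseline titer category and the randomization strata: a valid analysis that could be made more precise at little cost

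*SAP*

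**What the plan says.** SAP 6.1.1.3.1 compares Groups 1 and 3 combined with Groups 2 and 4 combined, one month after Vaccination 2. It uses intervals for the difference in "4-fold rises and composite responses, calculated by the Miettinen and Nurminen procedure". No strata, weights or covariates are named there or in protocol 9.4.1. The eight ACWY intervals (SAP 6.1.1.1.1 and 6.1.1.2.1) are likewise "calculated by the Miettinen and Nurminen procedure", run separately in naïve and experienced participants.

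SAP 5.2.1.1 sets the 4-fold hurdle by baseline category. The first rule begins "For participants with a baseline hSBA titer below the LOD" and asks for 1:16. From LOD to below LLOQ the hurdle is four times LLOQ; at or above LLOQ it is four times the participant's own titer. The MenB composite is defined in the same section from post-vaccination titers alone.

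SAP 2.2 stratifies randomization by prior vaccination history and adds: "Additionally, randomization will be stratified by geographic region".

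SAP 5.3.2 does use these factors in its missing-data models. Geographic location is a model term, and for 4-fold responses "the GLIMMIX will use baseline hSBA titer as covariate". Those models are optional, are triggered only when at least 10% of a group lacks titers for reasons other than withdrawal, and run in the mITT population.

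**The concern.** For the four MenB 4-fold endpoints the hurdle depends on where the participant starts. With Table 13 of the SAP, A22 (LOD 1:4, LLOQ 1:16) needs 1:16 from below LOD but 1:64 from the middle category. The other three strains need 1:16 and 1:32. Baseline category is therefore a natural candidate predictor of response. Its titer is already needed to compute the endpoint, so adjusting for it costs no data and loses no participant from those four analyses.

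All 13 lower limits must exceed -10% for the primary objectives to succeed (protocol 9.1.2 and 9.1.3), so the least powered intervals set the chance of success. In protocol Table 9 these are B24 (95.64%), the composite (97.80%) and A22 (98.03%). If baseline category or the strata predict response, an adjusted interval is narrower and a chance imbalance in them no longer shifts the estimate.

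**Working it through.** **Inputs.** Protocol 9.1.3: tests "at a 2-sided level of 0.05 for each of the endpoints". Margin -10 points. Protocol 9.2.1: "With 360, 180, 540, and 270 evaluable participants in Groups 1, 2, 3, and 4, respectively", so MenB compares 360+540 = 900 with 180+270 = 450. Reference rates are from protocol Table 9, with an assumed difference of 0. R2 is an assumption: the documents give no baseline-category shares and no response rates by category, region or ACWY history.

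**Step 1: reproduce the plan's power.** Score-test formula: power = Φ[(0.10 − 1.96·s0)/s1], where s1 uses the assumed rates and s0 the rates fitted under a difference of -10 points. For B24:
- s1 = √[0.645 × 0.355 × (1/900 + 1/450)] = 0.02763
- fitted rates 60.84% and 70.84%, so s0 = √[0.6084 × 0.3916/900 + 0.7084 × 0.2916/450] = 0.02690
- power = Φ[(0.10 − 0.05273)/0.02763] = Φ(1.711) = 95.65% (stated 95.64%)

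The same formula gives A22 98.04% (stated 98.03%), the composite 97.81% (97.80%) and B44 99.94% (99.94%). The MenB product is 91.65% (stated above 91.63%). ACWY-naïve is 99.96% and experienced 99.46%, so the ACWY factor is 0.9996 × 0.9946 = 0.9942. Combined: 0.9165 × 0.9942 = 91.1% (stated above 91.0%). Exact enumeration of the Miettinen-Nurminen limits gives 91.6%. The plan's power therefore belongs to the unadjusted analysis and does not rely on adjustment.

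**Step 2: adjust.** Multiply both variances by (1 − R2) for the MenB endpoints and leave ACWY unchanged. Combined power is the MenB power times 0.9942.

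| R2 | B24 | A22 | Composite | MenB, all five adjusted | Combined | MenB, composite unchanged | Combined |
|---|---|---|---|---|---|---|---|
| 0% | 95.65% | 98.04% | 97.81% | 91.65% | 91.1% | 91.65% | 91.1% |
| 2% | 95.98% | 98.22% | 98.01% | 92.34% | 91.8% | 92.15% | 91.6% |
| 5% | 96.45% | 98.47% | 98.29% | 93.31% | 92.8% | 92.86% | 92.3% |
| 10% | 97.17% | 98.85% | 98.70% | 94.79% | 94.2% | 93.93% | 93.4% |

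The B24 half-width, 1.96·s1·√(1 − R2), falls from 5.41 to 5.36, 5.28 and 5.14 points.

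**Step 3: what R2 might be.** For two categories with share q and response gap g, R2 = q(1 − q)g²/[p(1 − p)], with p(1 − p) = 0.645 × 0.355 = 0.2290 for B24.
- q = 10%, g = 20 points: 0.0036/0.2290 = 1.6%
- q = 20%, g = 30 points: 0.0144/0.2290 = 6.3%
- q = 30%, g = 40 points: 0.0336/0.2290 = 14.7%
- Region at 80/20: a 5-point gap gives 0.0004/0.2290 = 0.2%, a 10-point gap 0.0016/0.2290 = 0.7%

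The shares and gaps are illustrative.

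**Step 4: check for harm.** B24 was simulated (900 v 450, 40,000 trials, three baseline categories by two regions, standardized difference). Crude v adjusted power was 95.4% v 95.3% with no prognostic value, 95.4% v 95.9% at R2 = 3.8% and 95.5% v 97.5% at R2 = 13.7%. Coverage was about 95% for both methods throughout. A separate B24 simulation gave one-sided type I error of 2.3–2.6%.

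**The case against.** The strongest reply is that nothing is broken. The crude interval covers correctly, the stated power reproduces without adjustment, and protocol 9.2.1 would accept combined power above 85% under reduced enrollment. Allocation is 2:1 in both ACWY strata (360/180 and 540/270), so pooling over them does not confound the MenB comparison. All of this stands. A reader might infer that the primary analysis is wrong or underpowered; the documents do not support that.

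The benefit is also assumed. A different hurdle by category does not by itself imply a different response rate. This stands too, and is why a range starting at zero is shown.

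A reader might extend the point to all 13 intervals. That fails on size: ACWY power is already above 99.4%, and nonresponders are few. At planning rates, naïve MenA has about 180 × 4.2% ≈ 8 in Group 2. Reading Table 8's reference rate as the comparator's, experienced MenW has about 270 × 3% ≈ 8 in Group 4. Splitting these across strata adds fragility for almost no return.

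A reader might also assume that baseline is known for every evaluable participant. SAP section 4 requires a Visit 1 blood draw but no valid baseline titer. For 4-fold rises a missing baseline already makes the endpoint missing. For the composite it does not, so stratifying the composite by baseline without a missing-data rule would drop people from a coprimary analysis.

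Finally, the change is more than SAP wording, because protocol 9.4.1 names the method.

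**Conclusion.** The point holds as an efficiency recommendation for the five MenB intervals. Combined primary power would rise from about 91.1% to between 91.6% and 94.2% if R2 is 2–10%; the lower end assumes that the composite gains nothing. If the factors do not predict response, the gain is nil and the loss negligible (95.4% v 95.3% for B24). Almost all of the gain comes from B24, A22 and the composite. Region contributes little by itself; the reason to include it is that it was a randomization stratum.

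The figures rest on the protocol's planning rates, full evaluable numbers, multiplying endpoint powers as the protocol does, and a common R2 across the adjusted MenB endpoints. The documents give no R2, so they do not show that material precision is being lost, only that the plan forgoes the chance to recover it.

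**What to change.** Before unblinding, prespecify a single method for the MenB endpoints in SAP 6.1.1.3.1 and in the protocol 9.4.1 text that names the interval: a risk difference standardized to the pooled covariate distribution, which keeps the marginal estimand.

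- **Four 4-fold endpoints:** adjust for region, ACWY history and the strain's baseline category (below LOD; LOD to below LLOQ; at or above LLOQ), with a stated rule for merging sparse categories.
- **Composite:** adjust for region and ACWY history. If baseline status is added, give participants with a missing baseline titer their own category so that nobody is dropped.
- **Sensitivity:** keep the crude Miettinen-Nurminen interval.
- **ACWY intervals:** leave unadjusted.

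The margin, population and data collection do not change, and standard software suffices. The cost is the SAP text, the merging rule and probably a protocol amendment, since protocol section 9 and SAP section 2 require major changes to a primary analysis to be reflected in one.
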